12.2 Action to be Taken if Pregnancy Occurs in a Female Partner

If the partner of a study subject becomes pregnant within 90 days of the last dose of study drug, the pregnancy will be reported to the clinical unit within 48 hours of the subject's knowledge of the pregnancy. The Investigator will attempt to collect pregnancy information on any female partner of a randomized male study subject who becomes pregnant while participating in this study.

After obtaining the necessary signed informed consent from the female partner directly, the Investigator will record pregnancy information on the appropriate form and submit it to Indivior or designated representative within 24 hours of learning of the partner's pregnancy. The partner will also be followed to determine the outcome of the pregnancy and information on the status of

Confidential Page 62 of 108

INDV-2000 Clinical Study Protocol: INDV-2000-102 Indivior 09 May 2023

the mother and child will be forwarded to Indivior or designated representative. Generally, follow-up will be no longer than 6 to 8 weeks following the estimated delivery date. Any premature termination of the pregnancy will be reported regardless of foetal status (presence or absence of anomalies) or indication for procedure.

Confidential Page 63 of 108

13 DATA MANAGEMENT

13.1 Data Collection and Management

Data will be entered into subject eCRFs in a validated, access-controlled Clinical Data Management System (CDMS) and will be combined with other data captured centrally outside of the eCRF in a secure computing environment. Clinical data will be collected and managed in accordance with a study-specific data management plan to ensure that integrity of the data is maintained. Adverse events and medical history will be coded using the Medical Dictionary for Regulatory Activities (MedDRA). Prior and concomitant medications will be coded using the World Health Organization (WHO) Drug Dictionary. Completed eCRFs (including data queries and audit trail) will be retained by Indivior. Electronic copies of completed eCRFs will be sent to the Investigator for their records. Subject identifiers will not be collected or transmitted to Indivior, according to Indivior standards and procedures.

13.1.1 Database Quality Assurance

Subject eCRFs will be reviewed and checked for omissions, apparent errors and values requiring further clarification using computerized and manual procedures. Data queries requiring clarification will be generated programmatically and/or manually and addressed by the investigational site. Only authorized personnel will make corrections to the eCRFs, and all corrections will be documented in the CDMS audit trail.

13.1.2 Source Documents

The Investigator is responsible for the quality of the data recorded in the eCRFs. The data recorded must be a complete and accurate account of the subject's record collected during the study.

Study data are not to be gathered directly onto the eCRF but must be gathered onto primary source documents at the clinical site. Completion of source documents will precede the completion of the eCRF. Source documents may be electronic, hard copy, or a combination of both and are defined as the results of original observations and activities of a clinical investigation. Source documents will include, but are not limited to, progress notes, electronic data, screening logs and recorded data from automated instruments. All source documents pertaining to this study will be maintained by the Investigator and made available for direct inspection by the authorized study personnel outlined in the ICF. The eCRF will be considered the source document for individual eCRF elements such as study-specific scales if those data are collected directly onto an eCRF.

Confidential Page 64 of 108

INDV-2000 Indivior Clinical Study Protocol: INDV-2000-102 09 May 2023

14 STATISTICS

14.1 General Procedures

This section describes the sample size, analysis populations and planned analyses for primary, secondary and exploratory endpoints and for safety assessments. A comprehensive statistical analysis plan (SAP) will be developed to detail the statistical methodology for all aspects of the planned analyses. The SAP will be approved after the protocol is finalized and before the database is locked. Any deviations from the analyses described below will be identified in the SAP (and subsequently the CSR). Any unplanned analyses not described in the SAP will be identified in the CSR.

Data will be listed and summarized separately for Parts I, II and III of the study. For Parts I and II, data will be summarized by dosing cohort for active treatment and for placebo subjects combined over all dosing cohorts. Continuous variables will be summarized using descriptive statistics such as means, standard deviations (SD), medians, minimums and maximums. Categorical variables will be reported as frequency counts and the percentage of subjects in corresponding categories. Individual subject data will be presented in data listings. Data listings will include all data collected from enrolled subjects.

For change from baseline calculations, baseline will be defined as the last measurement taken prior to administration of IMP (INDV-2000 or placebo for Parts I and II, and INDV-2000 for Part III). For blood pressure and numeric ECG parameters, triplicate means will be used for baseline.

14.2 Sample Size

Part I (2 cohorts) and Part II (2 cohorts): Each cohort will be composed of 12 healthy volunteers (9 receiving active and 3 placebo). A total of 48 healthy male and female volunteers are planned to participate in both parts. Study subjects who are randomized but do not receive study drug will be replaced.

Part III: A single group of up to 16 treatment seeking subjects with OUD are planned to participate.

The sample sizes are not based on formal power calculations because the study is designed to provide preliminary descriptive assessments of the safety, tolerability and PK for INDV-2000. The sample sizes used are typical for studies of this nature and should be adequate to assess the parameters described.

14.3 Analysis Populations

14.3.1 Safety Population

The Safety Population is defined as subjects who received at least one dose of IMP.

Confidential Page 65 of 108

14.3.2 Run-In Safety Population

The Run-In Safety Population is defined as subjects who received at least one dose of study drug during the Part III run-in period.

14.3.3 Pharmacokinetic Population

The PK analysis population is defined as subjects who received at least one dose of INDV-2000, have an adequate number of PK samples collected to derive any PK parameter, and have no protocol deviations that would significantly alter plasma concentration of INDV-2000.

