Part II: Double-blind, placebo-controlled, randomized, multiple ascending dose study for 28 days of dosing with INDV-2000 in healthy volunteers. The screening period is up to 28 days. In each cohort, healthy volunteers will reside at the clinical unit from the evening of Day -1 to the morning of Day 8. Doses will be administered twice daily during Days 1-7. Healthy volunteers will be discharged after the morning dose administration on Day 8 except in case the Investigator judges it appropriate to retain the healthy volunteer to address safety concerns until resolution. Healthy volunteers will continue twice daily self-administration of INDV-2000 at home (except for in-clinic days) from Days 9 through 28. Healthy volunteers will return to the clinical unit for outpatient visits on Days 10, 15, 22 and 28 for safety assessments and PK samples. The EOS visit will be performed on the morning of Day 35 which is one week after the last dose. Male participants will complete a safety phone call 90 days after their last dosing day to assess any new pain, swelling or nodular lesions in the scrotum. This may be modified based on full evaluation of data from Part I in healthy volunteers. Two cohorts are planned, where each cohort will utilize a different dose, and all healthy volunteers within the same cohort will receive the same dose. Dose escalation decisions for Part II, Cohorts 1 and 2 will be based on a blinded review of TEAEs, concomitant medications, vital signs, ECGs, clinical laboratory test results and PK data from Days 1-7 of the prior cohort(s).

Part III: Part III dose determination will follow a blinded review of TEAEs, concomitant medications, vital signs, ECGs, clinical laboratory test results, and PK data from Part I, Cohorts 1 & 2, Part II, Cohort 1, and Part II, Cohort 2 Days 1-7. This part is an open-label study in OUD treatment seeking individuals. The screening period is up to 35 days. After screening, if check-in criteria are met, treatment seeking OUD subjects will enter the in-clinic portion of the study. First, subjects will initiate a run-in period with SUBOXONE SL film daily for 6 days. On Day -1 of the study, subjects must be stabilized on a SUBOXONE SL film dose between 8 mg/2 mg and

Confidential Page 28 of 108

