14.7.2 Secondary Endpoints

Secondary endpoints for Parts I and II will be PK parameters of INDV-2000 following dosing on Days 1 and 7, and Day 28 (Part II). PK parameters will be summarized as descriptive statistics for the PK Population and will comprise C_{max}, T_{max} and AUC_{0-24 or 0-12} for INDV-2000.

Confidential Page 66 of 108

There are no secondary endpoints for Part III.

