### 1.1. Objectives and Endpoints

Each study objective is presented in [Table 2](#) with associated estimands. Intercurrent events occur after treatment starts and either preclude the observation of an endpoint or affect its interpretation. For the intercurrent event of study discontinuation, the principal stratum strategy will be used for pharmacokinetic (PK) endpoints in that only subjects with an adequate amount of PK data will be included in the PK population; for all other endpoints, the while-on-treatment strategy will be used since data will be collected only up to end of study (EOS) or study discontinuation. Other potential intercurrent events in this study are prohibited medications and lifestyle restrictions detailed in protocol sections 9.6.2 and 9.6.3, respectively. Possible strategies for these intercurrent events are treatment policy (intervent event is ignored), while on treatment (data collected after the event is ignored), and principal stratum for PK endpoints (subject is excluded from the PK population), to be decided by the sponsor on a case-by-case basis.

[figure not shown]

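### The PK Population's deviation clause has no time limit, so a late home-dosing deviation in Part II can drop unaffected in-clinic Day 1 and Day 7 values from the summaries

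*Protocol*

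**What the plan says.** - **Population.** Protocol 14.3.3 defines one PK Population, by subject. A member must have had INDV-2000, must "have an adequate number of PK samples collected to derive any PK parameter", and must "have no protocol deviations that would significantly alter plasma concentration of INDV-2000". SAP Table 3 repeats the definition for Part III. Neither text says when the deviation must occur or which profile it must touch.
- **Use.** Protocol 14.7.2 sets the secondary endpoints as "PK parameters of INDV-2000 following dosing on Days 1 and 7, and Day 28 (Part II" only), namely Cmax, Tmax and AUC, and states that "PK parameters will be summarized as descriptive statistics for the PK Population". Protocol 14.12 does not, in general, impute missing data.
- **Part II schedule.** Under Protocol 4.1, "healthy volunteers will reside at the clinical unit from the evening of Day -1 to the morning of Day 8". Self-administration at home runs from Day 9, apart from clinic visits. Appendix 2 puts the single Day 28 dose in clinic.
- **Size.** "Each cohort will be composed of 12 healthy volunteers (9 receiving active and 3 placebo"). Sections 5.1 and 14.2 replace only randomized subjects who were never dosed.
- **SAP 1.1 (Part III only).** For prohibited medications and lifestyle restrictions it lists three possible strategies, to be chosen by the sponsor case by case: ignore the event, ignore data collected after it, or "principal stratum for PK endpoints (subject is excluded from the PK population").

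**The concern.** The endpoints come from separate profiles on separate days, but the exclusion acts on the whole subject. In Part II, most doses are taken at home after the Day 1 and Day 7 profiles are complete. A prohibited CYP3A4 drug in Week 3, or enough missed home doses to change exposure significantly, may spoil Day 28. It cannot change a concentration measured two weeks earlier, yet the definition removes all three days from the summaries.

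The definition also treats similar subjects differently. A volunteer who drops out on Day 10, with adequate samples and no deviation, keeps the Day 1 and Day 7 values, because data for any one parameter are enough. A volunteer who stays and has a qualifying deviation in Week 3 loses both.

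What is at stake is precision in cohorts of nine, and summaries of the best-controlled days that depend on conduct after Day 8. Shortfall at home is foreseen: Protocol 14.5 plans a flag for fewer than 80% of expected doses, reported separately for outpatient dosing in Part II.

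**Working it through.** **1. Headcount.** 4 cohorts × (9 + 3) = 48, which matches the protocol's total in 14.2. Active subjects who dose at home: 2 × 9 = 18, all in Part II. One subject is 1/9 = 11% of a cohort.

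**2. Share of dosing after the protected profiles.** Scheduled Part II doses are 27 × 2 + 1 = 55. Home doses on Days 9–27 are 19 × 2 = 38, less the three clinic morning doses on Days 10, 15 and 22, which leaves 35 (35/55 = 64%). If the Day 8 evening dose is also taken at home, it is 36 (65%).

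**3. Chance of losing subjects.** The documents give no rate of qualifying deviations. Let p be an assumed rate per subject during home dosing, with subjects independent.

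- P(at least 1 of 9) = 1 − (1 − p)^9
- P(at least 2 of 9) = 1 − (1 − p)^9 − 9p(1 − p)^8

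| Assumed p | At least 1 of 9 | At least 2 of 9 | At least 1 of 18 |
|---|---|---|---|
| 5% | 37% | 7% | 60% |
| 10% | 61% | 23% | 85% |
| 20% | 87% | 56% | 98% |

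**4. Effect on precision.** The readable plan does not call for an interval around a geometric mean; it serves here only as a yardstick. The log-scale half-width is t(0.975, n − 1) × s/√n, with s = √ln(1 + CV²). The CV is assumed, but the widening relative to n = 9 does not depend on it.

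| n per cohort | Factor at CV 30% | Factor at CV 50% | Log-scale widening vs n = 9 |
|---|---|---|---|
| 9 | ×/÷ 1.25 | ×/÷ 1.44 | – |
| 8 | ×/÷ 1.28 | ×/÷ 1.48 | 8.8% |
| 7 | ×/÷ 1.31 | ×/÷ 1.55 | 20.3% |

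The rows must be matched to the right probability: at least one loss goes with n = 8, and n = 7 needs two losses.

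**5. Current rule against a per-profile rule.** If k subjects in a cohort have a qualifying deviation after Day 8, the current definition leaves 9 − k on Days 1, 7 and 28. Exclusion by profile leaves 9 on Days 1 and 7, and 9 − k on Day 28 if every such deviation affects that profile.

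**The case against.** The strongest reply is that the detail may lie where it cannot be read. Protocol 14.8, the sampling windows in Appendix 5 and the SAP's PK methodology are blacked out, and no SAP for Parts I and II is among the documents. A profile-level rule could sit in any of them. That stands as a reason to check. Such a rule would, however, conflict with 14.3.3 as written, so the passages would still need reconciling.

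Several stronger readings are tempting, and the documents do not support them:

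- **Every home-dosing lapse triggers exclusion.** The deviation must be one that would significantly alter concentration. A single missed dose may not qualify, and the readable text gives no threshold.
- **SAP 1.1 confirms whole-subject exclusion for the study.** The SAP covers Part III only, and the exclusion wording is one of three options.
- **A prohibited drug on Day 11 of Part III necessarily removes the Day 3 and Day 9 data.** It may. The option to ignore only later data would keep them. Part III dosing is also in clinic, and Part III has no secondary endpoints.
- **The data are deleted.** Protocol 14.1 keeps all data from enrolled subjects in listings; only the summaries lose them.
- **An accumulation analysis is damaged.** None appears among the readable endpoints.
- **Dose escalation is compromised.** Escalation rests on a review of Day 1–7 data from prior cohorts at the time, not on the final PK Population.

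It is also fair to say that the analysis is descriptive and has no power basis, and that SAP 4 and 5.6.4 already call for population classification before database release and identification of deviations before lock in Part III.

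**Conclusion.** The point holds for the two Part II cohorts, 18 active subjects in all. As written, 14.3.3 read with 14.7.2 drops Day 1 and Day 7 parameters because of later deviations that cannot have affected them. This is a stated rule with an avoidable cost, not merely a missing detail.

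The cost is moderate. One lost subject widens a cohort's log-scale interval by about 9%, and two by about 20%. How likely that is depends wholly on the assumed rate of qualifying deviations. The early-day summaries also become conditional on later conduct; the documents do not allow the size or direction of any resulting bias to be estimated. No hypothesis test is affected.

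For Part III the conclusion is weaker: the case-by-case choice in SAP 1.1 makes loss of earlier profiles possible, and SAP Table 3 does not mention that choice. The change should be made because it is nearly free, subject to the check of the unreadable sections.

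**What to change.** 1. In Protocol 14.3.3 and SAP Table 3, define the PK Population as subjects with at least one INDV-2000 dose and at least one derivable PK parameter.
2. Move the deviation clause to the profile: leave a profile out of the summaries only if a deviation before or during it would significantly alter INDV-2000 concentrations in that profile.
3. Decide exclusions before unblinding in Parts I and II and before database lock in Part III. Because Protocol 9.1.3 lets the sponsor team unblind a cohort after its escalation decision, those who decide should still be blinded. List every excluded profile with its reason.
4. Align SAP 1.1 with the new wording, so that the handling of prohibited medications for PK endpoints follows the same rule.
5. Check the PK analysis section and any Part I/II SAP for a profile-level rule, and reconcile it with 14.3.3.

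The cost is about a sentence in each document and a per-profile flag in the PK analysis data set. The downside is that n will differ between study days, which the tables should show.

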14.4 Demographic and Baseline Characteristics

Indivior

09 May 2023

Demographic and baseline characteristics (e.g., sex, race, age, weight, height, BMI) will be summarized for the Safety and PK Populations, and separately for screen failures and run-in failures.

14.5 Extent of Exposure

Exposure will be summarized for the Safety Population. Exposure parameters will include total number of doses, dose duration, percentage of expected number of doses, and a binary variable for number of doses < 80% of expected. For Part II, percentage of expected doses and the binary variable will be summarized both overall and separately for in-patient vs. outpatient dosing. For Part III, exposure will be summarized for both INDV-2000 and buprenorphine.

14.6 Prior and Concomitant Medications

Prior and concomitant medications will be summarized by WHO Drug Dictionary medication class and standardized name.

14.7 Study Endpoints

14.7.1 Primary Endpoints

The primary endpoints for Parts I, II and III are the incidence, severity and relatedness of TEAEs; treatment-emergent SAEs (TESAEs); TEAEs leading to discontinuation; and fatal TEAEs. The primary endpoints will be assessed from first IMP dose through the final follow-up and will be summarized for the Safety Population as descriptive statistics only.

[figure not shown]
14.7.2 Secondary Endpoints

Secondary endpoints for Parts I and II will be PK parameters of INDV-2000 following dosing on Days 1 and 7, and Day 28 (Part II). PK parameters will be summarized as descriptive statistics for the PK Population and will comprise C_{max}, T_{max} and AUC_{0-24 or 0-12} for INDV-2000.

Confidential Page 66 of 108

There are no secondary endpoints for Part III.

14.7.3 Exploratory Endpoints

Confidential Page 67 of 108

14.8 Pharmacokinetic Analysis

Indivior 09 May 2023

Confidential Page 68 of 108

14.9 Safety Assessments

Safety parameters will be summarized for the Safety Population and will comprise TEAEs, laboratory evaluations, vital signs, 12-lead ECG findings, physical examination findings and C-SSRS assessments.

14.9.1 Treatment-Emergent Adverse Events (TEAEs)

A TEAE is defined as an AE with start date/time at or after dosing with IMP. The number and percentage of subjects reporting TEAEs will be presented for each treatment by MedDRA system organ class (SOC) and preferred term (PT), each in descending order of frequency among all subjects in the given part of the study (then alphabetically in case of ties).

Incidence and number of study drug-related TEAEs, TESAEs, study drug-related TESAEs, TEAEs leading to death, TEAEs leading to IMP discontinuation, and TEAEs leading to IMP interruption will be presented both in an overall summary table and by SOC and PT. Included in the overall summary table will be incidence and number of severe TEAEs and TEAEs with grade 3 or higher toxicity grade (applicable for Parts I and II only). TEAE incidence will also be summarized by maximum severity within SOC and PT. Incidence of TEAEs will be summarized by PT only (not SOC) in descending order of incidence among all subjects (within study part).

In summaries by severity and relationship to study drug, if more than one TEAE is coded to the same PT for the same subject, the subject will be counted only once for that PT using the most severe/most related occurrence. Missing severity, toxicity, and relatedness will be queried until resolution.

Non-TEAEs and, for Part III, run-in AEs in the Run-In Safety Population will be summarized separately.

Separate listings will be presented for TEAEs, TESAEs, TEAEs leading to IMP interruption or discontinuation and TEAEs leading to death.

14.9.2 Laboratory Evaluations

Laboratory evaluations will be summarized as observed values and changes from baseline by analysis visit. Normal/abnormal shifts from baseline will also be summarized.

14.9.3 Vital Signs

Vital signs (blood pressure, heart rate, respiratory rate, temperature) will be summarized as observed values and changes from baseline by analysis visit. For SBP and DBP, baseline will be defined as the mean of triplicate measurements.

Confidential Page 69 of 108

INDV-2000 Indivior Clinical Study Protocol: INDV-2000-102 09 May 2023

14.9.4 12-Lead Electrocardiogram

Numeric 12-lead ECG parameters will be summarized as observed values and changes from baseline by analysis visit, with baseline defined as the mean of triplicate measurements. ECG interpretation will be summarized by visit as a categorical variable, with baseline interpretation defined as the majority of the triplicate assessments; if there is no majority, the Sponsor will be notified and will provide a baseline interpretation based on a review of the data.

14.9.5 Physical Examination

Clinically significant physical examination changes from screening will be reported as AEs; therefore, there will be no separate listings or summaries of physical examination findings.

14.9.6 Columbia-Suicide Severity Rating Scale

The composite endpoints Suicidal Ideation and Suicidal Behaviour will be derived from the following 10 binary C-SSRS questions, reordered from the actual scale to facilitate the derivation:

Question 1	Wish to be Dead	
Question 2	Non-specific Active Suicidal Thoughts	
Question 3	Active Suicidal Ideation with Any Methods (Not Plan) without Intent to Act	
Question 4	Active Suicidal Ideation with Some Intent to Act, without Specific Plan	
Question 5	Active Suicidal Ideation with Specific Plan and Intent	
Question 6	Preparatory Acts or Behaviour	
Question 7	Aborted Attempt	
Question 8	Interrupted Attempt	
Question 9	Actual Attempt (non-fatal)	
Question 10	Completed Suicide	

Suicidal Ideation is derived as "yes" if any of Question 1-5 has a "yes" response. Suicidal Behaviour is derived as "yes" if any of Question 6-10 has a "yes" response. If there are zero "yes" responses and at least one question has a missing response, the derived composite will be missing. Suicidal Ideation and Suicidal Behaviour will be summarized as a categorical variable by analysis visit.

